#### Go to Rule 4.

c) Else, if at least one (but not all) non-target lesion has a status of "Unequivocal Progression", the responses may be limited to Non-CR/Non-PD, PD, NE (ie, responses of CR, NA are not permitted). (*Note: No response has been eliminated as an option here.*)

#### Go to Rule 5.

- 4. a) If all non-target lesions have a status of "Non-evaluable" and/or "Not Done" is selected, responses may be limited to NE.
  - b) Else, if no non-target lesions have a status of "Non-evaluable" and "Not Done" is not selected, responses may be limited to Non-CR/Non-PD (ie, responses of CR, PD, NE, NA are not permitted).
  - c) Else, if at least one (but not all) non-target lesion has a status of "Non-evaluable" and/or "Not Done" is selected, the responses may be limited to Non-CR/Non-PD, NE

(ie, responses of CR, PD, NA are not permitted). ■ (*Note: No response has been eliminated as an option here.*)

- 5. a) If all non-target lesions have a status of "Non-evaluable" and/or "Not Done" is selected, responses may be limited to NE.
  - b) Else, if no non-target lesions have a status of "Non-evaluable" and "Not Done" is not selected, responses may be limited to Non-CR/Non-PD, PD (ie, responses of CR, NE, NA are not permitted).
  - c) Else, if at least one (but not all) non-target lesion has a status of "Non-evaluable" and/or "Not Done" is selected, the responses may be limited to Non-CR/Non-PD, PD, NE (ie, responses of CR, NA are not permitted).

(*Note: No response has been eliminated as an option here.*)

If a subject has a missing tumor status at a disease assessment for 1 or more non-target lesions, radiologic disease progression will be determined if the remaining non-target lesions qualitatively demonstrate unequivocal progression (or if other criteria for PD are met).

#### **DERIVATION OF DISEASE RESPONSE AS PER RECIST 1.1**

Disease response will be programmatically derived on the data collection instrument using RECIST 1.1 criteria based upon target lesion response, non-target lesion response, and new lesion data. Missing values in any of target lesion response, non-target lesion response, and new lesion data will result in the disease response not being derived.

- CR Complete Response
- PR Partial Response
- SD Stable Disease
- PD Progressive Disease
- NE Non-evaluable

| Target Lesion | Non-Target Lesion Response      | New Lesion | Derived RECIST                  |
|----------------------|---------------------------------|------------|---------------------------------|
| Response             |                                 |            | Disease Response         |
| CR                   | CR or NA                        | No         | CR                              |
| CR                   | Non-CR/Non-PD or NE             | No (or NE) | PR                              |
| PR                   | CR or Non-CR/Non-PD or NE or NA | No (or NE) | PR                              |
| SD                   | CR or Non-CR/Non-PD or NE or NA | No (or NE) | SD                              |
| PD                   | Any                             | Any        | PD                              |
| Any                  | PD                              | Any        | PD                              |
| Any                  | Any                             | Yes        | PD                              |
| NE                   | CR or Non-CR/Non-PD or NE or NA | No         | NE                              |
| NA                   | CR                              | No         | CR                              |
| NA                   | Non-CR/Non-PD                   | No         | SD (Non-CR/Non-PD) a |
| NA                   | NE or NA                        | No (or NE) | NE                              |
| NA                   | CR or Non-CR/Non-PD             | NE         | SD (Non-CR/Non-PD) a |

<sup>a Per RECIST 1.1, "SD (Non-CR/Non-PD)" is preferred over "SD" for non-target disease since SD is increasingly used as endpoint for assessment of efficacy in some trials so to assign this category when no lesions can be measured is not advised.

If a subject has a missing tumor measurement at some assessment(s) for 1 or more target or a missing tumor status at some assessment(s) for 1 or more non-target lesions and criteria for PD are not otherwise met, an overall response of NE will be assigned for the assessment(s).

#### 3.3.5.2 irRECIST Derivations

#### **DERIVATION OF TUMOR BURDEN RESPONSE**

Tumor burden will be programmatically derived on the data collection instrument once irRECIST criteria are applied to the site personnel recorded target lesion and new lesions included in tumor burden measurements.

- irCR Complete Response
- irPR Partial Response
- irSD Stable Disease
- irPD Progressive Disease
- irNE Non-evaluable
- irNA Not Applicable (set value for all post-baseline disease assessments only if no target lesions are identified at baseline)

The derivation for tumor burden response is as follows (please note the order of the algorithm below is important):

- 1. If "Any Target Lesions Present" equals "No" on the *Target Lesions Baseline* CRF, then all post-baseline "Tumor Burden Response" equals "irNA".
- 2. Else, if "Percent Change from Nadir Sum of Diameters" is greater than or equal to 20% and the absolute increase from the nadir (defined as the "Total" for each Post-Baseline DA minus the "Nadir Sum of Diameters") is greater than or equal to 5 mm, then "Tumor Burden Response" equals "irPD".
- 3. Else, if "Not Done" is selected, or "Measurement" is left blank, or "Lesion no longer Measureable" is selected and equal to "NE", or "Lesion Intervention" is selected for any target lesion identified at baseline or new lesions included in the tumor burden, then "Tumor Burden Response" equals "irNE".
- 4. Else, if "Total Non-Lymph Node" equals "0" and all lymph node target lesion and new lesion included in the tumor burden "Measurements" are less than "10" individually, then "Tumor Burden Response" equals "irCR".
- a. Note: This step requires examining "Measurements" separately for Target lesions and new lesion included in the tumor burden with "Lymph Node" equal to "Yes" and "No".
- 5. Else, if "Percent Change from Baseline Sum of Diameters" is less than or equal to 30%, then "Tumor Burden Response" equals "irPR".
- 6. Else, "Tumor Burden Response" equals "irSD".

If a subject has a missing tumor measurement for lesions included in tumor burden at a disease assessment for 1 or more target lesions and/or new lesions included in tumor burden, the sum of diameters (longest for non-nodal lesions, short axis for nodal lesions) will be reported for the remaining target lesions and new lesions included in tumor burden. These data will be used to indicate radiologic disease progression if the sum of diameters for the observed lesions increases at least 20% from the nadir sum of diameters of all lesions and demonstrates at least a 5 mm absolute increase from the nadir sum of diameters of all lesions, in spite of the missing data (or if other criteria for irPD are met).

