## 3.4.2 Additional Analyses of the Efficacy Endpoints

Disease Response will also be assessed based on an application of immune-related Response Evaluation Criteria in Solid Tumors (irRECIST) (Nishino et al, 2013) to investigator assessed tumor measurements. All new lesions meeting measureable criteria will be included in the Tumor Burden. Objective Response by irRECIST is defined as immune-related complete response (irCR) or immune-related partial response (irPR) with confirmation required occurring no fewer than 4 weeks after initial documentation of irCR or irPR. If an irPR or irCR that is pending confirmation is designated at an assessment followed by 1 or more non-evaluable assessments or assessments of irSD, response may be confirmed thereafter Disease Control - 8 by irRECIST is defined as confirmed irCR, confirmed irPR, or immune-related stable disease (irSD) (maintained for ≥ 8 weeks). A similar definition applies

to Disease Control - 24. Duration of irSD is defined as the time from randomization (dose expansion) / the first dose of IP (dose escalation) until the first documentation of disease progression or death due to any cause, whichever occurs first, and will allow for the protocoldefined disease assessment window of 3 days. Concordance/discordance between RECIST 1.1 and irRECIST disease assessment will be summarized in frequency table.

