#### **DERIVATION OF DISEASE RESPONSE AS PER IRRECIST**

Disease response will be programmatically derived on the data collection instrument using irRECIST criteria based upon tumor burden response and non- tumor burden response data. Missing values in any of tumor burden response or non-tumor burden response data will result in the disease response not being derived.

Possible values include:

- irCR Complete Response
- irPR Partial Response
- irSD Stable Disease
- irPD Progressive Disease
- irNE Non-evaluable
- Abs Absent
- PI Present / Indeterminate

| Tumor Burden | Non-Tumor Burden        | Derived irRECIST        |  |  |
|--------------|-------------------------|-------------------------|--|--|
| Response     | Response                | Disease Response        |  |  |
| irCR         | Absent                  | irCR                    |  |  |
| irCR         | Present / Indeterminate | irPR                    |  |  |
| irPR         | Any                     | irPR                    |  |  |
| irSD         | Any                     | irSD                    |  |  |
| irPD         | Any                     | irPD                    |  |  |
| irNE         | Any                     | irNE                    |  |  |
| irNA         | Absent                  | Absent                  |  |  |
| irNA         | Present / Indeterminate | Present / Indeterminate |  |  |

Note: Non-tumor burden response only factors into the derived irRECIST disease response in the case of irCR vs irPR.

If a subject has a missing tumor measurement at some assessment(s) for 1 or more target lesions and/or new lesions included in tumor burden or a missing tumor status at some assessment(s) for 1 or more non-target lesions and/or new lesions not included in tumor burden and criteria for irPD are not otherwise met, an overall response of irNE will be assigned for the assessment(s).

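### The irRECIST rules give subjects without baseline target lesions no category that can count as response, disease control or progression, so a confirmed complete disappearance becomes an irRECIST non-response

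*SAP*

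**What the plan says.** In SAP section 3.3.5.2, under the derivation of tumor burden response, one permitted value is "irNA Not Applicable (set value for all post-baseline disease assessments only if no target lesions are identified at baseline". Step 1 of the algorithm assigns it, and the SAP states of the steps: "please note the order of the algorithm below is important". The steps that could return irPD, irNE, irCR, irPR or irSD come afterwards.

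The irRECIST disease response table has two rows for these subjects, "irNA | Absent | Absent" and "irNA | Present / Indeterminate | Present / Indeterminate". A note below it reads "Non-tumor burden response only factors into the derived irRECIST disease response in the case of irCR vs irPR". A sentence after the table assigns irNE when lesion data are missing and irPD is not otherwise met.

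Section 3.4.2 says: "Objective Response by irRECIST is defined as immune-related complete response (irCR) or immune-related partial response (irPR", with confirmation required. Disease control adds only irSD. On new lesions it says: "All new lesions meeting measureable criteria will be included in the Tumor Burden". The derivation of non-tumor burden response uses non-target lesions and only those new lesions that are outside the tumor burden.

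The RECIST 1.1 table in section 3.3.5.1 resolves the same subjects to CR, SD (Non-CR/Non-PD), PD or NE.

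**The concern.** Two labels come out of the irRECIST table that no endpoint definition uses. A subject with only non-target disease stays in the As-treated denominator (section 3.4.1) but cannot enter the numerator of irRECIST response or disease control, whatever happens to the disease.

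New lesions raise a second problem. A measurable one is assigned to the tumor burden, which is fixed at irNA for these subjects, and is left out of the non-tumor burden response. Neither part of the derivation registers it.

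At stake are the irRECIST comparison of the arms (section 2.1.3, objective 6) and the RECIST 1.1 versus irRECIST concordance table (section 3.4.2). That table should show differences between the criteria, not differences caused by an unmapped label.

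**Working it through.** The SAP states no figure that depends on this rule, so the check traces the two derivations for subjects with no target lesions. Inputs are the RECIST 1.1 table (3.3.5.1), step 1 of the tumor burden algorithm, the definition of non-tumor burden response and the irRECIST table (all 3.3.5.2), and the endpoint definitions (3.4.2).

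Four non-target states crossed with three new-lesion states give 4 × 3 = 12 cases. The irRECIST column is what the table returns.

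| Non-target response | New lesion | RECIST 1.1 | irRECIST table |
|---|---|---|---|
| CR | none | CR | Absent |
| CR | measurable | PD | Absent |
| CR | non-measurable | PD | Present / Indeterminate |
| Non-CR/Non-PD | none | SD (Non-CR/Non-PD) | Present / Indeterminate |
| Non-CR/Non-PD | measurable or non-measurable | PD | Present / Indeterminate |
| PD | none, measurable or non-measurable | PD | Present / Indeterminate |
| NE | none | NE | Present / Indeterminate (irNE if the missing-data sentence applies) |
| NE | measurable or non-measurable | PD | Present / Indeterminate (irNE if the missing-data sentence applies) |

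Across all 12 cases the table yields only two values. irCR, irPR, irSD and irPD never occur.

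**Response.** In row 1, once confirmed, the subject is a RECIST 1.1 responder. The irRECIST value *Absent* is neither irCR nor irPR, so the subject is a non-responder, and it is outside disease control too.

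**New lesion.** Rows 1 and 2 return the same irRECIST value, although in row 2 a measurable lesion has appeared. Step 2, which tests growth of the sum, is never reached. If it were reached, a 30 mm lesion arising from a nadir of 0 mm would give an absolute increase of 30 mm (the criterion is at least 5 mm) but a percent change of 30/0, which is undefined. The rule therefore needs a stated convention as well as access to step 2.

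**Size.** One subject is 1/40 = 2.5 points in the combination arm or 1/20 = 5 points in the nivolumab arm at the planned maximum. The number of such subjects is not given. Assuming 1 to 3 misclassified in one arm, the range is 2.5 to 7.5 points (n = 40) or 5 to 15 points (n = 20). With none it is zero. Recoding a scan like row 2 as irPD moves neither rate, because it is not a response or disease control under either label. It changes only the concordance cell.

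**Internal conflict.** The note quoted above limits non-tumor burden to separating irCR from irPR, yet in both irNA rows it alone fixes the result. The non-tumor burden text says progression will be determined from unequivocal progression when a status is missing. Section 3.3.5.4, which covers irRECIST, dates progression from non-target lesions and from the first new lesion. No row of the irRECIST table turns either into irPD.

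**The case against.** The strongest reply is that the separate labels are deliberate. They are listed among the possible values and have their own rows, and with no target lesions the baseline sum is zero, so percent change has no meaning. This explains why a separate label exists. It does not explain how the label counts: section 3.4.2 is silent, and the RECIST 1.1 table in the same SAP resolves its own not-applicable rows.

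A reader might infer that irRECIST here misses progression whenever a measurable new lesion appears. The SAP does not support that. Even with target lesions such a lesion only adds to the tumor burden: 30 mm is below a 20% increase whenever the nadir sum exceeds 30/0.20 = 150 mm. PD on RECIST 1.1 without irPD can be a genuine difference between the criteria. The narrower point stands: without target lesions, growth of that lesion can never lead to irPD.

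A reader might also infer that these subjects can receive no ir-category at all, or that the SAP ignores progression outside target lesions. irNE remains available for missing data, and the non-tumor burden text and section 3.3.5.4 do speak of such progression, although the table does not carry it out.

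Finally, the eligibility criteria are in the protocol, which is not at hand. If they require measurable disease, this branch may be empty. That is a fair limit on importance. The SAP nevertheless provides for these subjects in both algorithms.

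**Conclusion.** The point holds as a minor defect in an exploratory analysis. For subjects without baseline target lesions, the stated rules turn a confirmed complete disappearance into an irRECIST non-response and hide a measurable new lesion from both components. The effect on the irRECIST response or disease control rate is 2.5 or 5 points per misclassified subject, taking arms of 40 and 20, and nothing if no such subject is enrolled. For persisting, non-progressing non-target disease, the disease control effect also depends on whether SD (Non-CR/Non-PD) counts as SD under RECIST 1.1, which section 3.4.1.3 does not say. The primary RECIST 1.1 response rate is unaffected.

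**What to change.** 1. In the irRECIST table, map irNA with *Absent* to irCR only when no measurable new lesion is present. Count it, once confirmed, in irRECIST response and disease control. An unconditional mapping would label a subject with a measurable new lesion as irCR.
2. Restrict step 1 to assessments with no measurable new lesion. Once one exists, do not return *Absent*, and apply the step 2 growth rule to the sum of new lesions with a stated convention for the zero baseline. Taking the sum at first appearance as the reference is one option: 30 mm would then need to reach 36 mm (20% and 6 mm). Declaring irPD at first appearance would be stricter than the rule for subjects with target lesions.
3. Label the remaining irNA with *Present / Indeterminate* results Non-irCR/Non-irPD, excluding unequivocal non-target progression. Treat them in disease control exactly as RECIST 1.1 SD (Non-CR/Non-PD) is treated, and state what that treatment is. Plain irSD would go against the caution in the RECIST 1.1 table's footnote.
4. Reconcile the non-tumor burden text, the irRECIST table with its note, and section 3.3.5.4 on progression outside target lesions.

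The cost is a few lines in the SAP and a small programming change, with no new data.

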#### **DERIVATION OF NON-TUMOR BURDEN RESPONSE**

Non-tumor burden will be programmatically derived on the data collection instrument once irRECIST criteria are applied to the site personnel recorded non-target lesion and new lesions not included in tumor burden.

- Absent Response assigned if all non-target lesions and new lesions not included in the tumor burden statuses equal Absent
- Present / Indeterminate Response assigned if any of the non-target lesions or new lesions not included in the tumor burden statuses do not equal Absent

If a subject has a missing tumor status at a disease assessment for 1 or more non-target lesions and/or new lesions not included in tumor burden, radiologic disease progression will be determined if the remaining non-target lesions and new lesions not included in tumor burden qualitatively demonstrate unequivocal progression (or if other criteria for irPD are met).

#### **DERIVATION OF DISEASE RESPONSE AS PER IRRECIST**

Disease response will be programmatically derived on the data collection instrument using irRECIST criteria based upon tumor burden response and non- tumor burden response data. Missing values in any of tumor burden response or non-tumor burden response data will result in the disease response not being derived.

Possible values include:

- irCR Complete Response
- irPR Partial Response
- irSD Stable Disease
- irPD Progressive Disease
- irNE Non-evaluable
- Abs Absent
- PI Present / Indeterminate

| Tumor Burden | Non-Tumor Burden        | Derived irRECIST        |  |  |
|--------------|-------------------------|-------------------------|--|--|
| Response     | Response                | Disease Response        |  |  |
| irCR         | Absent                  | irCR                    |  |  |
| irCR         | Present / Indeterminate | irPR                    |  |  |
| irPR         | Any                     | irPR                    |  |  |
| irSD         | Any                     | irSD                    |  |  |
| irPD         | Any                     | irPD                    |  |  |
| irNE         | Any                     | irNE                    |  |  |
| irNA         | Absent                  | Absent                  |  |  |
| irNA         | Present / Indeterminate | Present / Indeterminate |  |  |

Note: Non-tumor burden response only factors into the derived irRECIST disease response in the case of irCR vs irPR.

If a subject has a missing tumor measurement at some assessment(s) for 1 or more target lesions and/or new lesions included in tumor burden or a missing tumor status at some assessment(s) for 1 or more non-target lesions and/or new lesions not included in tumor burden and criteria for irPD are not otherwise met, an overall response of irNE will be assigned for the assessment(s).

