#### 3.3.5.4 Assignment of Dates of Disease Progression or Disease Response

For all analyses of endpoints resulting from an application of modified RECIST 1.1 (dose escalation phase), RECIST 1.1 (expansion phase) to investigator assessed tumor measurements, and irRECIST, there may be cases in which disease assessments span a series of dates. For establishing the start date of a subsequently confirmed response in which the disease assessment spans multiple days, the response date assigned will be the latest date of evaluations corresponding to the disease assessment. The date of latest assessment will also be assigned for a mid-study assessment showing SD as the date assigned for the purposes of censoring of duration of response, TTP and PFS.

The date of PD will be the first date at which any objective diagnostic test provides data indicating PD. Specifically, the date of PD will be the earliest of the following 3 dates:

- Date of PD as indicated by target lesions: If PD is triggered by a change in sum of diameters of target lesions, and the dates of evaluation of the target lesions vary for the same assessment, assign the first evaluation date among target lesions.
- Date of PD as indicated by non-target lesions: If the dates of evaluation of the non-target lesions vary for the same assessment, assign the first evaluation date for which any non-target lesion exhibits a status of Unequivocal Progression.
- Date of PD as indicated by new lesions: If multiple new lesions are identified and the dates of evaluation for the new lesions vary for the same assessment, assign the first evaluation date for which any new lesion is detected.

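### The irRECIST missing-data sentences contradict the irRECIST response table: when a non-target or unmeasured new-lesion status is missing, text and table give different responses

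*SAP*

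**What the plan says.** Section 3.4.2 plans the irRECIST analysis: "Disease Response will also be assessed based on an application of immune-related Response Evaluation Criteria in Solid Tumors (irRECIST"). It covers confirmed response, disease control at 8 and 24 weeks, and a concordance table against RECIST 1.1. Section 2.1.3, objective 6, makes the comparison of arms by irRECIST exploratory.

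Section 3.3.5.2 combines a tumor burden response (target plus measured new lesions) with a non-tumor burden response (non-target plus unmeasured new lesions). The latter has two levels, Absent and Present/Indeterminate. The second is defined as: "Response assigned if any of the non-target lesions or new lesions not included in the tumor burden statuses do not equal Absent". In the response table, tumor burden of irPR, irSD, irPD or irNE passes straight through whatever the non-tumor burden response. The note below the table confirms this: "Non-tumor burden response only factors into the derived irRECIST disease response in the case of irCR vs irPR".

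Three other sentences in that section deal with missing data:

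- Non-tumor burden part, when a status is missing for at least one lesion: "radiologic disease progression will be determined if the remaining non-target lesions and new lesions not included in tumor burden qualitatively demonstrate unequivocal progression".
- Opening of the disease-response part: "Missing values in any of tumor burden response or non-tumor burden response data will result in the disease response not being derived".
- Closing paragraph of the disease-response part, which includes a missing non-target or unmeasured new-lesion status: "criteria for irPD are not otherwise met, an overall response of irNE will be assigned for the assessment(s").

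Section 3.3.5.4, which names irRECIST in its scope, also dates progression from non-target lesions: "assign the first evaluation date for which any non-target lesion exhibits a status of Unequivocal Progression".

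**The concern.** A derivation table and its missing-data rules should return one response per scan. Here the table leaves no route from non-target data to irPD or irNE, while the sentences around it create both. The result is also perverse: unequivocal non-target progression is ignored when every status is recorded, but counts as progression when one status is missing.

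At stake are irRECIST response, irRECIST disease control and the concordance table. Concordance is the most exposed. Under RECIST 1.1 a non-target response of PD always gives PD, so some apparent disagreement between the two criteria could come from the paragraph the programmer followed. With 40 and 20 subjects planned (section 2.4), one subject whose best response or disease-control status changes moves an arm's rate by 1/40 = 2.5 or 1/20 = 5 percentage points. The study is open-label (section 2.3), so a choice left to programming could be made with knowledge of treatment.

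**Working it through.** The plan states no figure on this point, so the check sets the rules side by side. Three inputs were varied: tumor burden response, whether at least one non-target or unmeasured new-lesion status is missing, and whether the remaining such lesions unequivocally progress.

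One step is interpretive. A missing status is not Absent, so the two-level definition makes the scan Present/Indeterminate and the table then applies.

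| Tumor burden | Non-target / unmeasured new lesions | Table and note | Missing-status progression sentence | Closing irNE paragraph |
|---|---|---|---|---|
| irSD | one missing, rest progress | irSD | irPD | irNE on a strict reading |
| irPR or irCR | one missing, rest progress | irPR | irPD | irNE on a strict reading |
| irSD | one missing, no progression | irSD | silent | irNE |
| irPR or irCR | one missing, no progression | irPR | silent | irNE |
| irSD | all recorded, progression | irSD | silent | silent |
| irPR or irCR | all recorded, progression | irPR | silent | silent |
| irPD | any | irPD | no conflict | no conflict |
| irNE | one missing, rest progress | irNE | irPD | irNE on a strict reading |
| irNA | one missing, rest progress | Present/Indeterminate | irPD | irNE on a strict reading |
| irNA | one missing, no progression | Present/Indeterminate | silent | irNE |

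The strict reading takes the irPD criteria to be those of the table alone. If they include the missing-status progression sentence, the irNE paragraph yields to irPD, because it applies only when irPD is not otherwise met.

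Four things follow.

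1. Each conflicting scan gets two labels, or in some cases three on the strict reading. The sentence on underived responses adds a further outcome if a missing lesion status counts as missing non-tumor burden response data.
2. The two text rules for irPD and irNE can be reconciled with each other. Neither can be reconciled with the table and note as written.
3. Rows 1 and 5 have the same tumor burden and the same kind of progression. Row 5, with complete data, is irSD. Row 1, with less data, is irPD by the text.
4. The note is inexact for the irNA rows, where non-tumor burden alone decides the result.

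The RECIST 1.1 derivation has closely similar missing-status wording. Its progression sentence works there because RECIST 1.1 has a non-target PD level and a table row that turns it into PD. The irRECIST table has neither. That the wording was carried over is an inference, but it would explain the mismatch.

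**The case against.** The best defense is that the missing-data sentences are specific overrides: the table covers recorded statuses, and the text covers missing ones. The irNE paragraph comes after the table and yields to irPD, so an orderly reading exists. That is possible, but the SAP does not state it. The note is worded without exception, and the two-level coding already places a scan with a missing status. The override reading also keeps the odd result that losing one status turns irSD into irPD.

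A second objection is that section 3.3.5.4 only assigns dates when an assessment spans several days and is shared by all the criteria. This stands. Its non-target bullet does not make a scan irPD. It only offers a date for an event that the irRECIST table cannot produce.

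Three stronger readings are tempting, and the SAP does not support them.

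- A reader might infer that one scan could be irPD, irSD, irPR or irNE. It cannot: tumor burden fixes whether the table gives irSD or irPR. The four labels arise only across different scans.
- A reader might infer that every subject with stable measured burden and unequivocal non-target progression switches between irSD and irPD. The progression sentence applies only when a status is missing. On a complete scan the response rules give one label.
- A reader might put a percentage on the affected progressions from an assumed share that are non-target only. That share would still have to be combined with how often a status is missing. The SAP gives neither.

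**Conclusion.** The irRECIST rules are inconsistent as written, in two places: progression in the remaining lesions when a status is missing, and the response assigned to a missing status. For measured burden of irCR, irPR or irSD, the conflict is irPD or irNE from the text against the single value, irSD or irPR, from the table. Scans with burden of irNE or irNA can conflict too, as the comparison shows. Only scans with a missing non-target or unmeasured new-lesion status are affected, and their number cannot be estimated from the SAP.

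The conclusion rests on reading a missing status as not Absent and on the absence of any stated precedence. The consequence is limited to exploratory irRECIST response, disease control and concordance. The primary RECIST 1.1 ORR, the Go/NoGo criteria and RECIST 1.1 PFS do not use these rules. This is a minor point that is nearly free to correct.

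**What to change.** Let the table and note govern, and make the rest agree:

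- Delete the unequivocal-progression sentence from the non-tumor burden part.
- Limit the irNE and not-derived sentences to missing target or measured new-lesion data, and say which of the two applies when.
- Reword the note to acknowledge the irNA rows.
- In section 3.3.5.4, state that under irRECIST the non-target bullet does not apply and that irPD is dated from the target and new lesions included in tumor burden. A date rule for measured new lesions must stay, because the target bullet speaks only of target lesions. Restricting the whole new-lesion bullet to RECIST 1.1 would leave irPD driven by those lesions undated.

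If the sponsor intends non-target progression to count, add an unequivocal-progression level to the non-tumor burden response and a table row giving irPD. Apply both to complete and incomplete scans alike, and state the order of precedence for a missing status.

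Either route costs a few lines of SAP text and one programming rule. It should be settled before the irRECIST outputs are programmed.
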